8.7 ADMINISTRATIVE STRUCTURE OF THE TRIAL

The trial is sponsored by Boehringer Ingelheim (BI).

A Coordinating Investigator is responsible to coordinate investigators at the different sites participating in this trial. Tasks and responsibilities are defined in a contract.

An extended SMC will be established for both part A and part B. The SMC shall operate under the principles specified in the SMC charter. The primary objective of the SMC is to ensure and protect the safety and well-being of the trial subjects and to regularly review the trial data and provide recommendation for the further conduct of the trial.

The SMC is a multidisciplinary group composed of the co-ordinating investigator, participating investigators (as deemed necessary) with treated subjects in the cohort that will be evaluated in the meeting (Part A only), members of the BI trial team and two experts independent from the BI trial / project team in the field of ophthalmology. The SMC members have been selected for their expertise in these areas, their knowledge of the management of subjects with DMI and their experience in clinical trials and SMC activities. Details of the SMC responsibilities and procedures are described in the SMC charter.

Relevant documentation on the participating (Principal) Investigators (e.g. their curricula vitae) will be filed in the ISF.

The investigators will have access to the BI web portal Clinergize to access documents provided by the sponsor.

BI has appointed a Clinical Trial Leader (CT Leader), responsible for coordinating all required activities, in order to

- manage the trial in accordance with applicable regulations and internal SOPs,
- direct the clinical trial team in the preparation, conduct, and reporting of the trial,
- ensure appropriate training and information of Clinical Trial Managers (CT Managers), Clinical Research Associates (CRAs), and investigators of participating countries.

The organisation of the trial in the participating countries will be performed by the respective local or regional BI-organisation (Operating Unit, OPU) in accordance with applicable regulations and BI SOPs, or by a Contract Research Organisation (CRO) with which the responsibilities and tasks will have been agreed and a written contract filed before initiation of the clinical trial.

Data Management and Statistical Evaluation will be done by BI according to BI SOPs.

Tasks and functions assigned in order to organise, manage, and evaluate the trial are defined according to BI SOPs. A list of responsible persons and relevant local information can be found in the ISF.

A central laboratory, central ECG, central ophthalmologic reading centre and an IRT vendor will be used in this trial. Details will be provided in corresponding manuals, available in the ISF.

Analyses of BI 765128 concentrations in serum will be performed at a qualified analytical laboratory or at another Contract Research Organization (CRO) with given authorisation by BI.

10. APPENDICES

10.1

[figure not shown]

Table 10.1: 3 Time schedule for optional [REDACTED] (Part B)

Trial Periods	Visit	Day	Time Point	Optional [REDACTED]
Treatment	2	1	Just before drug administration	X*
	3	29 (±3)		
	4	57 (±3)	Just before drug administration	X*
Follow-up	5	85 (±7)		
Follow-up	6	113 (±7)	Any time during the visit	X*
EOS	7	141 (±7)	Any time during the visit	X*

* Optional [REDACTED] samples are collected immediately before drug administration at Visits 2 and 4. At visits 6 and 7, when no drug is administered, the aqueous samples can be collected at any time during the visit.

**10.2 BENEFIT-RISK ASSESSMENT IN CONTEXT OF COVID-19
PANDEMIC FOR SUBJECTS PARTICIPATING IN TRIAL 1451-0001
INVESTIGATING BI 765128**

STUDY POPULATION

As per the Centers for Disease Control and prevention (CDC), people with serious chronic medical conditions, including diabetes and heart disease, might be at higher risk for severe illness from COVID-19.

BENEFITS AND RISKS CONCLUSIONS AND RECOMMENDATIONS

Currently, there is no evidence that based on the pharmacological mechanism and existing non-clinical data BI 765128 either may affect the immune system or increase the risk of progression of COVID-19 infection. BI 765128 is administered intravitreally using standard aseptic technique.

The low dosage of BI 765128 means the systemic exposure is expected to be very low.

Therefore, no change on the Benefit-Risk assessment of the compound in the context of the COVID-19 pandemic is foreseen.

The current study population is potentially at higher risk of COVID-19 infection due to background or concomitant diseases. Enrollment will start when the local situation allows, and appropriate risk mitigation measures (e.g. use of Personal Protective Equipment) will be implemented in line with local instructions and recommendations

The investigators will take the totality of information related to each single subject and the local COVID-19 situation into consideration when performing the individual benefit-risk assessment on a case-by-case basis. Considering all aspects, the investigator will decide upon each subject's (continued) participation in the trial. BI as the sponsor, where required, will support the investigator in their decision finding. It is acknowledged that the investigator may decide to implement protocol deviations where this protects the safety, wellbeing and/or is in the best interest of the subject.

DETAILS OF TRIAL PROCEDURES AT SELECTED VISITS

In situations where an individual subject is unable or unwilling to attend a clinic visit, the investigator must assess the risk-benefit for the individual subject and may decide to perform a visit remotely if this is in the best interest of the subject and if agreed with the sponsor. All COVID-19 related deviations from the original schedule of visits and procedures will be documented and the implications considered for the analysis of the trial data.

No trial specific SARS-CoV-2 testing will be performed. Testing will be performed in line with local standard procedures. In case of a confirmed infection appropriate measures e.g. for monitoring and quarantine will be implemented.

10.3 STATISTICAL APPENDIX

A BLRM with overdose control will be used to guide dose escalation in this study. The BLRM is introduced in Section 7.1, which also specifies the prior for the model. After subjects in each cohort have completed the evaluation period, the prior distribution will be updated through Gibbs sampling procedures with the accumulated DLE data from the evaluation period. Posterior probabilities for the rate of DLEs will be summarized from the BLRM. Selection of the next dose will be based on these probabilities as well as on other safety and laboratory data.

The purpose of this statistical appendix is to present performance metrics (operating characteristics) that illustrate the precision of the design in estimating the MFD (see Section 3.1) under various dose-toxicity relationships through computer simulation. These results are summarized in Table 10.3: 3. In addition, recommendations of the next dose level by the BLRM with overdose control principle are provided under various hypothetical outcome scenarios in early cohorts, to show how it facilitates on-study dose-escalation decisions (see Table 10.3: 1). For simplicity reasons, a cohort size of 3 subjects who are all evaluable is assumed.

Hypothetical data scenarios

Hypothetical data scenarios are shown in Table 10.3: 1. These scenarios reflect potential on-study data constellations and related escalation as allowed by the model and the planned dose groups. For each scenario, the probability of overdose for the current dose, as well as the next potential dose and related probabilities of target dosing and over-dosing are shown (probability of over-dosing: P(OD), probability of target dosing: P(TD)).

For example, scenario 1 represents the case that no DLE is observed in 3 subjects at the starting dose of [REDACTED]. In this case, the next planned dose permitted by the model is 1 mg.

In scenario 6, there is no DLE after the first 2 dose groups, which would allow the trial to continue to the next dose level. If no further DLE occurs in the trial (scenario 13), dose escalation would proceed to the [REDACTED] dose, with an additional cohort at that dose level at the end, i.e. overall 12 subjects.

Table 10.3: 1 Hypothetical data scenarios

Scenario	# Pat.	# DLE	[REDACTED]	[REDACTED]	[REDACTED]
1	3	0	[REDACTED]	[REDACTED]	[REDACTED]
2	3	1	[REDACTED]	[REDACTED]	[REDACTED]
3	3	2	[REDACTED]	[REDACTED]	[REDACTED]
4	6	1	[REDACTED]	[REDACTED]	[REDACTED]
5	6	2	[REDACTED]	[REDACTED]	[REDACTED]

Scenario		# Pat.	# DLE
6		3	0
		3	0
7		3	0
		3	1
7b		3	0
		6	1
7c		3	0
		6	2
8		3	0
		3	2
10		6	1
		3	0
11		6	1
		3	1
11b		6	1
		6	1
11c		6	1
		6	2
12		6	1
		3	2
13		3	0
		3	0
		6	0
14		3	0
		3	0
		6	1
15		3	0
		3	0
		6	2
16		3	0
		6	1
		6	0
17		3	0
		6	1
		6	1
18		3	0
		6	1
		6	2

Scenario	# Pat.	# DLE
19	6	1
	6	1
	6	0
20	6	1
	6	1
	6	1
21	6	1
	6	1
	6	2

*Non of the pre-specified dose levels is fulfilling the EWOC criterion

No higher dose level specified

Operating characteristics

Operating characteristics are a way to assess the long-run behaviour of a model by illustrating the precision of the design in estimating the MFD. Under an assumed true dose-toxicity curve, metrics such as the probability of recommending a dose with true DLE rate in the target interval can be approximated via simulation. Table 10.3: 2 describes 5 assumed true dose-toxicity scenarios which were used to assess the operating characteristics of the model. These scenarios reflect a wide range of possible cases as follows:

- Scenario 1: aligned with prior means
- Scenario 2: high-toxicity scenario
- Scenario 3: low-toxicity scenario
- Scenario 4: very high toxicity scenario
- Scenario 5: low-toxicity followed by high-toxicity

Table 10.3: 2 Assumed true dose-toxicity scenarios

Scenario	P(DLE)	[Redacted]			
		[Redacted]	[Redacted]	[Redacted]	[Redacted]
1: Prior Mean	P(DLE)	0.054	0.073	0.153	0.364
2: High Tox		0.154	0.173	0.243	0.464
3: Low Tox		0.005	0.007	0.053	0.264
4: Very high Tox		0.245	0.353	0.564	0.689
5: Low-High		0.005	0.007	0.243	0.464

The dose level 5 was added for technical reasons, since for simulations at least one dose with assumed true DLE rate in each toxicity interval was required

For each of these scenarios, 1000 trials were simulated. Each cohort consisted of 3 subjects and dose escalation complied with the following rule:

Escalate to the maximum dose which satisfies the overdose criterion and is $\leq 500\%$ increase from the current dose.

The MFD was considered reached if at least 12 subjects have been included in the trial and if at least 6 subjects have been evaluated at a dose level which was the model's recommendation for the next dose. The maximum allowed subject number for each trial was chosen as 18.

It was then assessed how often a dose was declared as MFD with true DLE rate in the targeted or in the overdosing range. Furthermore, the average, minimum and maximum number of subjects per trial and the average number of DLEs per trial are reported. Results are shown in Table 10.3: 3.

Table 10.3: 3 Simulated operating characteristics

Scenario	% of trials declaring a MFD with true DLE rate in		% of stopped trials*	# Subjects	# DLEs
		overdosing		Mean (Min-Max)	Mean (Min-Max)
1	94.1	2.0	3.9	10.99 (3 - 27)	1.21 (0 - 6)
2	76.2	0.6	23.2	11.39 (3 - 27)	2.14 (0 - 8)
3	99.0	0.8	0.2	9.32 (9 - 27)	0.33 (0 - 5)
4	15.1	18.1	66.8	10.10 (3 - 27)	3.40 (0 - 7)
5	99.9	0.0	0.1	11.84 (9 - 27)	1.37 (0 - 5)

* The stopped trials include early stopped trials (stopped due to too much toxicity), as well as trials that stopped because the maximum allowed subject number was reached before an MFD was found.

In scenario 1, which reflects the case that the true dose-toxicity is aligned with prior mean, 94.1% of the simulated trials declared a dose as MFD with true DLE rate in the targeted toxicity range. Note that 3.9% of the simulated trials stopped either because there was no MFD determined after 27 subjects had been observed or because of too high toxicity for the planned doses.

In scenario 2, the assumed dose toxicities is high. This results in a higher percentage of early stopped trials (about 23.2 %). In this case, about 76.2 % of the trials would end with an estimated MFD within the targeted range, and 0.6 % in the overdosing range.

In Scenario 3 (low-toxicity scenario), only 99.0 % of the trials declared a dose as MFD with true DLE rate in the targeted range. In 0.8 % of the trials, the estimated MFD was in the overdosing range.

Scenario 4 (very-high-toxicity scenario) shows the worst results, i.e. the highest number of stopped trials (66.8 %) and a low number of trials with estimated MFD (15.1 %) in the target range, as would be expected.

Scenarios 5 (low-high toxicity scenario) shows the best results, i.e. the lowest number of stopped trials (0.1 %) and a highest number of trials with estimated MFD (99.9 %) in the target range.

The mean subject numbers ranged from 9.3 subjects (Scenario 3) to 11.8 subjects (Scenario 5), and the maximum number of subjects was 27.

Overall, by reviewing the metrics presented in Table [10.3: 3](#), it can be seen that the model is generally conservative due to the overdose control criteria. In all scenarios, except for the very-high-toxicity case (scenario 4) the probabilities of recommending a dose with true DLE rate being at least 25%, $P(\text{DLE} \geq 25\%)$, as MFD are much smaller than the probabilities of recommending a dose with true $P(\text{DLE}) < 25\%$ as MFD.

R version 4.0.2 and Jags version 4.3.0 was used for data scenarios and simulations.

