7.6 DETERMINATION OF SAMPLE SIZE

Part A:

No formal statistical power calculations to determine sample size were performed for this explorative study. A Bayesian logistic regression model (BLRM) was used for guiding the dose escalation process (see Section [3.1](#) for details). For the SRD part, a minimum of 3 subjects and a maximum of 18 subjects will be expected for this trial based on the number of dose levels/cohorts that are tested (for details regarding the BLRM assumptions refer to appendix [10.3](#)). Fewer subjects might be needed based on the recommendation of the SMC. However, the actual number of subjects will depend on the number of dose cohorts tested. Based on the simulation study to evaluate operating characteristics of the BLRM, about 15 evaluable subjects are expected to be treated in the dose escalation part for the model to have reasonable operating characteristics relating to its MFD recommendation.

Part B:

In the publication Samara et al. [[R17-3318](#)] estimates for FAZ means and standard deviations (SD) were derived. The worst case was for PDR subjects with mean deep FAZ of 0.766 mm². The standard deviation of FAZ ranged from 0.112 mm² to 0.3402 mm² for disease categories from control to PDR. It is assumed that intra-individual variability is much lower than the inter-individual SD from Samara et al. because of the high correlation of the baseline and the FAZ values after treatment. Taking into account the high correlation, a SD of FAZ of 0.1 mm² seems to be reasonable to be used in calculation of risk probabilities. With 20 subjects in the BI 765128 [REDACTED] arm and 10 subjects in the sham arm, there is a likelihood of 81.7% of observing a treatment effect larger than 6% (a reduction of 0.0462 mm²) and a likelihood of 10.2% of observing a treatment effect smaller than 4% (a reduction of 0.0308mm²) when the assumed mean treatment difference is 10%. Assuming a mean treatment difference of 0% there is a likelihood of 12.3% observing a treatment effect larger than 6% and a likelihood of 78.7% of observing a treatment effect smaller than 4%.

8. INFORMED CONSENT, TRIAL RECORDS, DATA PROTECTION, PUBLICATION POLICY, AND ADMINISTRATIVE STRUCTURE

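### Protocol Table 10.3:3 was not produced by the rules stated for Part A: it shows up to 27 subjects against a cap of 18, and three mean sizes that a minimum of 12 makes impossible

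*Protocol*

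**What the plan says.** Protocol Section 10.3 reports 1000 simulated trials in each of five dose-toxicity scenarios, with cohorts of 3.

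- **Cap.** "The maximum allowed subject number for each trial was chosen as 18". Section 7.6 agrees for the trial itself: "a minimum of 3 subjects and a maximum of 18 subjects will be expected for this trial". Below Table 10.3:3, however, the text says that "3.9% of the simulated trials stopped either because there was no MFD determined after 27 subjects had been observed" or because of toxicity, and closes with "the maximum number of subjects was 27". Every row of the table shows a maximum of 27.
- **Minimum.** "The MFD was considered reached if at least 12 subjects have been included in the trial", with at least 6 of them at the recommended dose. Sections 3.1 and 7.1 set the same limits of 12 and 6 for the real trial.
- **Escalation.** The simulated rule is "Escalate to the maximum dose which satisfies the overdose criterion and is" no more than a 500% increase. Section 7.1 limits each step to the next planned dose and to 250%. The worked examples in 10.3 follow the stepwise path: in scenario 6 "there is no DLE after the first 2 dose groups, which would allow the trial to continue to the next dose level", and scenario 13 reaches the top dose "with an additional cohort at that dose level at the end, i.e. overall 12 subjects".

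**The concern.** Section 10.3 offers the table as evidence of how precisely the design finds the MFD. In a first-in-human trial, ethics committees and authorities may read it that way. A simulation capped at 18 cannot yield 27, and a design that declares nothing before 12 subjects cannot average 9.32 when almost every simulated trial declares an MFD. If the simulation could also jump past the middle dose, its subject numbers, dose path and event counts belong to another set of rules. They cannot then be cited as properties of Part A.

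**Working it through.** **1. Cap.** The stated cap is 18 (Sections 7.6 and 10.3). The reported maximum is 27 in all five rows and twice in the text. No calculation is needed.

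**2. Lowest possible mean size.** A trial that declares an MFD has at least 12 subjects. A stopped trial has at least one cohort of 3. So

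mean N ≥ (share declaring) × 12 + (share stopped) × 3.

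| Scenario | Declared (target + overdosing) | Stopped | Lower bound | Printed mean |
|---|---|---|---|---|
| 1 | 0.941 + 0.020 = 0.961 | 0.039 | 11.65 | 10.99 |
| 2 | 0.762 + 0.006 = 0.768 | 0.232 | 9.91 | 11.39 |
| 3 | 0.990 + 0.008 = 0.998 | 0.002 | 11.98 | 9.32 |
| 4 | 0.151 + 0.181 = 0.332 | 0.668 | 5.99 | 10.10 |
| 5 | 0.999 + 0.000 = 0.999 | 0.001 | 11.99 | 11.84 |

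Scenarios 1, 3 and 5 are impossible; scenarios 2 and 4 are not excluded. Simulation error cannot explain the gaps, because bound and mean describe the same simulated trials.

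In scenario 3 the printed minimum is 9. With cohorts of 3, P(N > 9) ≤ (9.32 − 9)/3 = 0.107, so at least 89% of trials ended at exactly 9 subjects. Only 0.2% were stopped, so most trials declared an MFD at 9.

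**3. Does the 500% rule allow a jump to the top dose?** The doses are redacted, but the prior in Section 7.1 gives their ratio as exp[(logit p_top − logit p_start)/exp(μ₂)]:

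- component 1: (0.02, 0.1, μ₂ = 0.052) gives 4.996
- component 2: (0.1, 0.3, μ₂ = −0.176) gives 5.001
- component 3: (0.001, 0.01, μ₂ = 0.362) gives 5.001

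The top dose is five times the start, a 400% increase: inside 500%, outside 250%, and not the next step. Relative doses of 0.2, 0.4 and 1 give prior overdose probabilities of 0.050, 0.072 and 0.192, against 0.050, 0.073 and 0.190 in Table 7.1:2, so the model is reproduced. After 0 of 3 DLEs at the start, the posterior overdose probability at the top dose is about 0.14, below the limit of 0.25. The simulated rule therefore goes straight to the top whenever the first cohort is clean: 0.995³ = 98.5% of trials in scenario 3 and 0.946³ = 84.7% in scenario 1.

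**4. Do the printed results show the jump?** Scenario 3 has DLE rates of 0.005, 0.007 and 0.053 at the planned doses and 0.264 at the added technical dose. Suppose no dose is skipped.

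- A 9-subject trial with 6 at its MFD has nobody at the top dose. Longer trials have at most N − 6 subjects at the top and technical doses together (mean ≤ 0.64) and N − 9 at the technical dose (mean ≤ 0.32). Mean DLEs ≤ 0.264 × 0.32 + 0.053 × 0.32 + 0.007 × 8.68 = 0.16.
- Ignoring the 6-subject rule: 3 × 0.005 + 3 × 0.007 + 3 × 0.053 + 0.32 × 0.264 = 0.28.

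The table prints 0.33, and the standard error over 1000 trials is about 0.013 to 0.017. Three subjects at the start plus six at the top give 3 × 0.005 + 6 × 0.053 = 0.333 with N = 9.

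**5. Recalculated means.** The technical dose is assumed to be twice the top dose (prior mean 0.366; Table 10.3:2 has 0.364). The two middle columns are simulations of 4000 trials per scenario. The last column is a range over exact enumeration and simulation, over the MFD wording, with or without the technical dose. In scenario 5 its upper end takes the third cohort at 6.

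| Scenario | Printed | 10.3 as written (12, 18, 500%) | Minimum 9, cap 27, 500% | Trial's rules (12, 18, next dose) |
|---|---|---|---|---|
| 1 | 10.99 | 12.89 | 11.31 | 12.7–13.3 |
| 2 | 11.39 | 11.65 | 10.90 | 11.4–11.9 |
| 3 | 9.32 | 12.16 | 9.68 | 12.2–12.3 |
| 4 | 10.10 | 9.26 | 9.18 | about 9–10 |
| 5 | 11.84 | 13.16 | 11.89 | 13.0–13.4 |

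The printed means do not follow from the rules in 10.3. They lie within one subject of a version with minimum 9, cap 27 and skipping; exact enumeration with minimum 9, a larger cap and skipping comes closer in scenarios 1 and 3 (10.95 and 9.34). That match is not exact: the largest simulated trial had 24 subjects, not 27.

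**The case against.** Four points can be made on the other side.

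- **The 500% rule is disclosed.** It is printed above the table, and 10.3 also discloses a simplified cohort size. This stands. The third item is a difference between two sections, of less weight than the cap and the minimum; step 4 shows only that the simulation followed its printed escalation rule.
- **Nothing in the trial turns on the table.** Real escalation follows Sections 3.1 and 7.1 with Safety Monitoring Committee review, and SAP Section 7 describes the model runs as already performed. This stands too. A reader might infer that real subjects skipped the middle dose; nothing in the documents says so.
- **The appendix is about MFD precision, and no percentage is shown to be wrong.** Correct. The MFD and stopping percentages move by several points with the wording of the MFD rule and the handling of the technical dose, so no change is claimed. A reader might infer an unsafe design; the documents do not support that.
- **The simulated design is not simply smaller.** A reader might infer so from scenarios 1, 3 and 5. But its cap is larger, scenario 2 is close to the trial's rules, and the printed scenario 4 mean is slightly above them.

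Section 7.6 refers to about 15 evaluable subjects on the strength of the simulation, while the table means run from 9.3 to 11.8. The sentence can be read as a size needed for good behaviour, so this is something to check, not a contradiction.

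The amendment history in Section 11 may explain the mismatch, but the point does not rest on it. Everything compared here is current text.

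**Conclusion.** The point holds, as a reporting matter. The cap and minimum findings need only the printed numbers and are certain. The jump past the middle dose rests on dose ratios implied by the printed prior; that Section 7.1 forbids it does not depend on the redacted doses.

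Under the trial's rules the maximum is 18. Mean size rises by about 1.7 to 2.3 subjects in scenario 1, 2.9 to 3.0 in scenario 3 and 1.2 to 1.6 in scenario 5. It is similar or slightly higher in scenario 2 and lower in scenario 4. These figures assume the relative doses and technical dose above, and mostly cohorts of 3. They leave out committee discretion and the stop after DLEs in the first two subjects at a new dose.

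The general conclusion of 10.3 probably stands: outside the very-high-toxicity scenario, an overdosing MFD is much less likely than one in target.

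**What to change.** - Re-run the simulation with at least 12 subjects, a cap of 18, at least 6 at the MFD, and escalation to the next planned dose only, by at most 250%.
- Give the third cohort its planned 6 subjects (Section 3.1), or state that cohorts of 3 are a simplification.
- Replace the 500% rule in 10.3 with that of 7.1, and say how the technical dose is handled.
- Replace Table 10.3:3 and the text that repeats its sizes and percentages.
- Check whether the figure of about 15 in 7.6 is still supported, and reword it if it is meant as a simulated mean.

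The cost is a short re-run and replacement text, with no extra subjects and no change to dosing. A protocol change needs ethics and authority approval (Section 8.1), so it can go into the next amendment. Because the Part A model runs are reported as done, a correction in the trial report would also serve.
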